Iatrogenic hyperinsulinemia's contribution to endothelial dysfunction early in the course of T1DM is uncharacterized. Impaired endothelial function has been consistently observed in prepubertal,(29) midpubertal,(6) and postpubertal pediatric patients,(8) as well as young(30) and middle-aged(7) adults with T1DM. Several lines of research suggest insulin may exert beneficial vascular effects by increasing endothelial nitric oxide (NO) synthase gene expression(31) and activity(32, 33) and stimulating NO release and vasodilation.(34-36) On the other hand, hyperinsulinemia may exert detrimental vascular effects by amplifying mitogenic activity of growth factors, increasing expression of endothelial adhesion molecules, and enhancing monocyte adhesion to the endothelium.(34, 37, 38) Induction of hyperinsulinemia in healthy subjects to concentrations matching basal insulin levels typically seen in T1DM drastically diminished flow-mediated dilation (FMD), a frequently-used technique to quantify endothelial function.(39) Further study suggested this effect was mediated *independent of insulin sensitivity*.(34) Thus, my primary outcome in Aim 2 will determine how much clinically driven changes in peripherally delivered insulin doses modify brachial artery endothelial function during the early course of T1DM. As a secondary objective of Aim 2, I will use the contrast-enhanced ultrasound (CEUS) technique(40) to measure insulin-induced microvascular recruitment in adult participants.

Therapies to lower hyperinsulinemia-mediated IR and endothelial dysfunction in T1DM are limited. To date, no study has attempted to improve IR or endothelial dysfunction by lowering the total daily dose of insulin (TDD_{insulin}). The dearth of these studies is partially related to concern that lowering TDD_{insulin} would worsen hyperglycemia. A diet that is lower in carbohydrates, however, is one approach to safely lower TDD_{insulin} without raising glycemia. Thus, in Aim 3, we will conduct a 2x2 crossover intervention study testing whether the reduction in TDD_{insulin} over a one-week low-carbohydrate diet (LCD) intervention will result in improved insulin sensitivity compared with one-week standard carbohydrate diet (SCD).

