To test this hypothesis, I will analyze the relationship (figure 1) between hyperinsulinemic exposure (quantified by average total daily dose of insulin, $TDD_{insulin}$) and insulin sensitivity (Aim 1) and early endothelial dysfunction (Aim 2) at multiple points in the progression of T1DM (figure 2). In a longitudinal study (T1DM SUBSTUDY in figure 2), I will study patients at three phases over the 12 months following diagnosis, initial diagnosis, honeymoon phase, and post-honeymoon phase. Each phase has distinct insulin exposure: 1) soon after diagnosis (STUDY1: $TDD_{insulin} \approx 0.5$ units/kg/day), 2) during partial clinical remission (PCR), a.k.a. "Honeymoon phase" (STUDY2: $TDD_{insulin} < 0.4$ units/kg/day), and 3) after emergence from PCR (STUDY3: $TDD_{insulin} > 0.6$ units/kg/day). Additionally, we will study healthy, matched, euglycemic control participants to assess the contribution of hyperinsulinemia to IR under four experimental conditions (CONTROL SUBSTUDY in figure 2): (i) endogenous insulin only (STUDY 4), (ii) overnight hyperinsulinemia (IV insulin infusion, STUDY 5), (iii) one week of mild hyperinsulinemia (glargine, STUDY 6), and (iv) both overnight insulin and one week of hyperinsulinemia (STUDY 7). To further test this hypothesis, I will conduct a 2x2 crossover intervention study in adults with T1DM testing whether the reduction in $TDD_{insulin}$ associated with a one-week, isocaloric low-carbohydrate diet (LCD) intervention will result in improved insulin sensitivity compared with one-week, isocaloric, standard carbohydrate diet (SCD) (STUDY B-C, figure 3).

T1DM SUBSTUDY (n=20)

CONTROL SUBSTUDY (n=20)

[figure not shown]

Figure 2: Schematic for STUDY visits. Est. = estimated.

PCR=partial clinical remission. $TDD_{insulin}$ = total daily dose of insulin

Specific Aim 1: Quantify the contribution of iatrogenic hyperinsulinemia to IR during the early course of T1DM. The hyperinsulinemic, euglycemic clamp technique will quantify insulin sensitivity at each STUDY visit. Although insulin sensitivity improves during PCR,(28) no study to date has determined how much iatrogenic hyperinsulinemia contributes to reduced insulin sensitivity during this time.

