5.3 Randomization

STUDY1-7 (Aims 1-2), include a longitudinal study of newly diagnosed T1DM patients during the first twelve months after diagnosis (T1DM SUBSTUDY, STUDY1-3) Because of the longitudinal nature of the T1DM substudy, no randomization process is needed for STUDY 1-3. The CONTROL SUBSTUDY investigates the effect of small doses of insulin in healthy, nondiabetic individuals over differing durations: one week (STUDY 5), one night (STUDY 6), both one week and one night (STUDY 7), and with no exogenous insulin at all (STUDY 4). Control participants will go through STUDY 4-7 in a random order. The study team will randomize participant into a treatment order group using a web-based randomization tool (<http://www.sealedenvelope.com>), a Microsoft Excel macro, or a randomization tool within Redcap.

STUDY B-C (Aim 3), is a random-order, 2x2 crossover study. On one arm, participants will consume a low-carbohydrate diet (LCD). On the other arm, participants will consume a standard carbohydrate diet (SCD). As shown in [figure 3](#), T1DM and control participants will be randomized into one of two treatment orders (“A” vs. “B”).

Random permuted blocks with a fixed size of 4 will be used to randomize patients into treatment order A (SCD then LCD) vs. treatment order B (LCD then SCD). The study team will randomize participant into a treatment order group using a web-based randomization tool (<http://www.sealedenvelope.com>), a Microsoft Excel macro, or a randomization tool within Redcap.

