6.0 Study Procedures

6.1 Research visits: STUDY1-7 (Aims 1-2)

All subjects will participate in a screening visit ([section 6.1.1](#)) then will participate in one of two substudies based on whether they are a participant recently diagnosed with T1DM (T1DM SUBSTUDY) or if they are a healthy control participant without T1DM (CONTROL SUBSTUDY). Figure 5 summaries the T1DM and CONTROL substudies.

[figure not shown]

Figure 5: Schematic for STUDY visits. Est. = estimated.

PCR=partial clinical remission. $TDD_{insulin}$ = total daily dose of insulin

1. Participants selected for the **T1DM SUBSTUDY (n=20)** will have a T1DM duration of less than one year. They will participate in three identical STUDY visits (STUDY1-3).
 - STUDY1 will occur within 1-3 months of diagnosis in most instances. In our practice, the initial starting total daily dose of insulin ($TDD_{insulin}$) upon diagnosis is usually 0.5 units/kg/day.(56) STUDY1 will require each participant's $TDD_{insulin}$ averaged over 5 consecutive days fall between 0.4-

0.6 units/kg/day, which is a common dosing range during the first 2-3 months after diagnosis.

- For participants to enter STUDY2, their mean TDD_{insulin} must be \leq 0.4 units/kg/day. This usually occurs between 3-6 months post-diagnosis.
- To enter STUDY3, the TDD_{insulin} must exceed or equal 0.6 units/kg/day, which usually occurs by 12 months post-diagnosis.

2. Participants selected for the CONTROL SUBSTUDY (n=20) will not have T1DM and have no chronic illnesses. They will participate in STUDY 4-7 (each CRC study visit follows the same protocol).

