6.1.2 Management Before and In Between STUDY 1-7 visits

Each T1DM participant's endocrinologist will manage his or her glycemic control and insulin doses before and between T1DM SUBSTUDY visits. The study team will review each T1DM SUBSTUDY study participant's insulin doses on at least a monthly basis between study visits.

Each CONTROL SUBSTUDY participant will take insulin glargine 0.2 u/kg/dose each day for seven days preceding STUDY 6 and 7 and an equal volume of a placebo injection (saline) prior to STUDY 4 and 5. The participant will be blinded to whether they are taking placebo or insulin glargine.

Although the study takes several measures to mitigate the possibility of hypoglycemia in these participants (section 7.1), the investigator will not be blinded to whether or not control participants are taking insulin prior to CONTROL SUBSTUDY participants. This enables the investigator to rapidly alter the course of the intervention in the event of hypoglycemia.

In the unlikely event severe hypoglycemia occurs (i.e. loss of consciousness or seizure due to hypoglycemia) blinding will be broken to ensure the patient's hypoglycemia is treated appropriately.

Approximately 10-14 days before STUDY visits 1-7, a study team member will contact the participant to remind them to:

1. Wear their CGM for at least the 7 days leading up to the STUDY visit for T1DM SUBSTUDY participants CONTROL SUBSTUDY participants will be reminded to wear either their study-supplied CGM or conventional capillary blood glucose monitor.
2. Record food and drink consumed for the 7 days leading up to the STUDY visit in their digital food log.

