10.1.2 Analysis Plan

The correlation between the independent variable TDD_{insulin} (averaged over 7 days prior to each STUDY visit) and the key dependent variable for each objective will be determined: GIR in Aim 1; %FMD and MVR in Aim 2. Several other explanatory variables could influence each specific aim's key dependent variable, however. For example, confounding variables might include hyperglycemia, hyperlipidemia, or the dependent variables in each aim could affect one another (e.g. insulin resistance could affect endothelial dysfunction). For this reason, I will use multivariable linear regression analysis to account for the effect of potential confounders, which include age, T1DM duration, glycemia (both from both CGM over 7 days and HbA1c), lipidemia (i.e. lipoprotein subclass sizes and particle concentrations), NEFA concentration, hypertension, BMI, body composition, and estrogen level.

The study accrual of 40 participants provides 3 to 4 degrees of freedom for a multivariable linear regression analysis. (i.e. TDD_{insulin} and 3 additional independent variables can be included in an adequately-powered model). To quantify the effect of potential confounders, unadjusted and adjusted linear regression models will be fit and compared for each Aim's primary outcome (GIR and %FMD). I will analyze changes in β -coefficients between unadjusted and adjusted models for scientifically significant differences.

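### In STUDY 1-3 the insulin dose is titrated to need, so a negative TDD-GIR slope can arise without any effect of dose on insulin sensitivity, and 10.1.2 should not use it to quantify a causal contribution

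*Combined protocol and SAP*

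**What the plan says.** Aim 1 in Section 2.0 is to "Quantify the contribution of iatrogenic hyperinsulinemia to IR during the early course of T1DM". Section 1.0 says Aim 2 will determine how much "clinically driven changes in peripherally delivered insulin doses modify brachial artery endothelial function during the early course of T1DM". Both are causal wordings.

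The analysis in Section 10.1.2 takes TDD, averaged over the seven days before each visit, as the independent variable. The correlation between it "and the key dependent variable for each objective will be determined: GIR in Aim 1; %FMD and MVR in Aim 2". Multivariable linear regression then adjusts for candidates that begin "age, T1DM duration, glycemia (both from both CGM over 7 days and HbA1c" and go on to lipids, NEFA, hypertension, BMI, body composition and estrogen. On model size, the section says: "The study accrual of 40 participants provides 3 to 4 degrees of freedom for a multivariable linear regression analysis". That count pools the 20 T1DM and 20 control participants.

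Three other places say where TDD comes from in the T1DM substudy:
- Section 6.1.2: each participant's "endocrinologist will manage his or her glycemic control and insulin doses before and between T1DM SUBSTUDY visits".
- Section 5.3: "Because of the longitudinal nature of the T1DM substudy, no randomization process is needed for STUDY 1-3".
- Section 6.1: visits are entered on TDD itself. STUDY1 needs 0.4-0.6 units/kg/day and STUDY2 at most 0.4. For STUDY3 the dose "must exceed or equal 0.6 units/kg/day, which usually occurs by 12 months post-diagnosis".

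In the control substudy, insulin is assigned and the order of STUDY 4-7 is random (Sections 5.3 and 6.1.2).

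**The concern.** GIR is the clamp measure of insulin sensitivity. At a given glucose target, a less sensitive person, or the same person in a less sensitive phase, needs more insulin. A dose managed to glucose then depends partly on the outcome that the regression tries to explain. The induced sign (higher TDD, lower GIR) is the one the hypothesis predicts, so the STUDY 1-3 slope cannot separate the hypothesis from its reverse.

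Section 10.1.2 recognises confounders and says that the outcomes may affect one another. It does not say that an outcome may affect the exposure. Adjusting for CGM glucose and HbA1c does not help, because at fixed glycemia a titrated dose tracks need more closely. C-peptide is drawn (Table 3) but is not a listed covariate. Adding it would account for residual secretion but would leave the path from sensitivity to dose open.

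The stake is the T1DM conclusion of Aim 1, and more weakly of Aim 2. A contribution of hyperinsulinemia could be reported when the true effect is zero.

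**Working it through.** **Plan's own figure.** Table 7, T1DM GIR row: n = 20, difference 1.3 mg/kg/min, SD 2.7, r 0.79, two-sided 5%. SD of the paired difference = 2.7 × √(2 × (1 − 0.79)) = 2.7 × √0.42 = 1.75. The noncentral t with 19 df gives power 0.883, against 0.88 stated. The inputs are usable, and the issue is not power.

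**Inputs for a zero-effect simulation.**
- From Table 7: 20 people, SD 2.7, r 0.79. Mean GIR 6.5, because 1.3 is given as about 20% and 1.3 / 0.20 = 6.5. Within-person SD = 2.7 × √(1 − 0.79) = 1.24.
- From Section 6.1: three visits per person.
- Assumed, because the documents give no figure: the titration exponent b, random dose variation of 15-30%, and phase mean doses of 0.5, 0.35 and 0.7 units/kg/day (chosen to fit the entry limits).

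**Model.** TDD = phase mean × (GIR / 6.5)^(−b) × exp(noise), with no effect of TDD on GIR. The test is the within-person slope of GIR on TDD, one-sided at 2.5% in the hypothesised direction. The spurious deficit is slope × 0.2, the gap between the 0.4 and 0.6 entry limits.

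**Results (share of studies rejecting a true null).**
- b = 0: 2-3%, so the test is calibrated.
- One common dose mean, phases ignored: 20-56% at b = 0.25 and 58-97% at b = 0.5, with a deficit of 0.4-1.2 mg/kg/min at b = 0.5.
- Phase means included: 11-15% at b = 0.25, 31-49% at b = 0.5 and 73-88% at b = 1. The deficit is about 0.1-0.3 mg/kg/min. Dose changes between phases that do not come from GIR dilute the slope.
- Phase means included, and half of the within-person GIR variance treated as clamp error: about 6% at b = 0.25 and 11-16% at b = 0.5. Measurement error in the clamp cannot drive the previous week's dose.
- All within-person variance treated as clamp error: about 2.5%, the nominal rate.

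Against Table 7's 1.3, the phased deficit is 0.1 / 1.3 = 8% to 0.3 / 1.3 = 23%. The runs carry no covariates. Adjusting for T1DM duration would take out part of the phase-driven dose change and so weaken the dilution.

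**Other analyses.** Section 10.1.2 does not say that the slope is within-person, so two alternatives matter. Here titration was linear and 10-75% of within-phase TDD variance (SD 0.10, assumed) was driven by sensitivity. At nominal 5% two-sided, the false-positive rate was 7-26% for the within-person slope. It was 12-96% for the paired low-versus-high contrast with visits gated at 0.4 and 0.6, and 59-100% for a regression on participant means.

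**Is the randomised contrast adequate?** Table 7 states power 0.92 for control GIR, C-BOTH versus C-0. SD of the difference = 3.5 × √0.42 = 2.27, and the paired t-test gives 0.98. The stated figure does not reproduce exactly, but it is not optimistic.

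**The case against.** Much of the plan already speaks of association. Section 10.1.2 calls the analysis a correlation, the Section 2.0 hypothesis is worded as an independent correlation, and Section 7.5.1 says association. Section 2.0 assigns the controls the task of assessing hyperinsulinemia's contribution under experimental conditions, and Table 7 powers that contrast separately. All of this stands, and it narrows the gap: 10.1.2 does not name the randomised contrast as the causal test, counts all 40 participants toward one TDD regression, and sits beside causal wording in Sections 1.0 and 2.0.

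The magnitude is also open to challenge. A reader might take the phase-free model and infer that the correlation will look like a hyperinsulinemia effect, with a spurious deficit close to Table 7's 1.3. The documents do not support that. They give no figure for how far TDD tracks sensitivity rather than remission, diet or dosing practice. The substudy is built on phases, which cut the rate, and some within-person GIR variation must be clamp error, which cuts it further.

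A reader might also infer that only STUDY 4-7 can support a causal claim. That overlooks Aim 3, which randomises diet order in adults with T1DM in order to lower TDD.

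**Conclusion.** The concern holds as a possibility of known direction and unknown size. Clinician-managed dosing, no randomisation and entry gated on TDD are all documented, and no listed covariate removes the path from sensitivity to dose. The direct loop concerns GIR. For %FMD and MVR it runs only through insulin resistance, a link that Section 10.1.2 itself raises.

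With zero true effect, the within-person false-confirmation rate is roughly 6-50% for exponents of 0.25-0.5 once phases are modelled, up to about 88% at exponent 1, and nominal if all within-person GIR variation is clamp error. The spurious deficit is about 0.1-0.3 mg/kg/min per 0.2 units/kg/day. These figures rest on the assumed exponents, dose noise and phase means. They show that the null is not protected and do not estimate the actual bias.

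The plan should be changed, because a randomised and separately powered test of the causal question already exists within it.

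**What to change.** In Section 10.1.2:
1. Analyse the T1DM and control substudies separately.
2. Make the randomised within-person STUDY 4-7 contrasts the test of the causal contribution in Aims 1-2, led by C-BOTH versus C-0. Define each condition by the insulin assigned, because Section 5.3 and Section 2.0 swap the descriptions of STUDY 5 and STUDY 6.
3. Report the STUDY 1-3 TDD slope as an association that may partly reflect insulin need, and state whether it is a within-person slope.
4. Align the causal wording in Sections 1.0 and 2.0 with this.

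Do not try to bridge the substudies by applying the control effect per unit of fasting insulin to the T1DM visits. Fasting insulin at STUDY 1-3 follows stopped or held home insulin and an overnight infusion adjusted to glucose (Sections 6.1.3.1 and 6.1.3.2, Appendix 1). It does not measure the previous week's exposure.

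No new visits or measurements are needed. The cost is a more cautious T1DM claim: causality would rest on healthy controls, with Aim 3's randomised diet comparison as the randomised evidence in T1DM.

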10.0 Statistical Considerations

10.1 STUDY 1-7 (Aims 1-2)

10.1.1 Sample Size Justification

My accrual goal is to obtain an adequate number of participants within both the T1DM SUBSTUDY (STUDY 1-3) and CONTROL SUBSTUDY (STUDY 4-7) to ensure greater than 80% statistical power ($1-\beta$) for a two-sided α -level of 5% for each specific aim's primary outcome. The sample size calculations used the best-available previously published descriptions of insulin sensitivity(28, 105) and %FMD(7, 30, 106-108) in T1DM. Table 7 summarizes these calculations.

Table 7: Key parameters for sample size calculations for T1DM and CONTROL substudies. n , δ , $1-\beta$, σ , and r represent the sample size, the expected minimum difference, statistical power, overall standard deviation, and longitudinal correlation, respectively, for each key outcome. * indicates calculations based on preliminary data as previously described. [†] The detectable differences for GIR of 1.3 to 2.2 mg/kg/min represent a 20% to 21% change in outcomes. [‡] The detectable differences for %FMD of 2.2% to 4.3% represent a 25% to 39% change in outcomes.

Aim	T1DM Substudy					Control Substudy						
	Key Outcome for Power Calculation	n	δ	$1-\beta$	σ	r	Key Outcome for Power Calculation	n	δ	$1-\beta$	σ	r
1	GIR between STUDY T ^{LO} vs. T ^{HI} in mg/kg/min	20	1.3	0.88	2.7	0.79	GIR between STUDY C ^{BOTH} vs. C ⁰ in mg/kg/min	20	2.2	0.92	3.5	0.79
2	%FMD between STUDY T ^{LO} vs. T ^{HI}	20	2.2%	0.88	4.3%	0.83	%FMD between STUDY C ^{BOTH} vs. C ⁰	20	4.3%	0.83	3.7%	0.83

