10.2 STUDY B-C (Aim 3)

10.2.1 Sample size justification

My accrual goal for STUDY B-C is to have a sufficient sample size to conduct multivariable linear regression with 4 degrees of freedom to quantify the effect of the independent variable, mean $TDD_{insulin}$, on the dependent variable, GIR during the last 30 minutes of the clamp study. At a minimum, 10 participants are needed per degree of freedom to conduct this analysis, thus, we will study 30 participants with T1DM and 10 control participants who are otherwise healthy.

Based on Del Prato et al.,(27) I anticipate participants completing the SCD arm will not see a change in GIR during the last 30 minutes of the clamp study compared to baseline, but will see an increase in GIR of at least 0.6 mg/kg/min after completing the LCD arm. This study also suggests the pooled standard deviation of GIR will be 0.8 mg/kg/min. If the true difference in the Δ GIR between LCD and SCD arms for the 30 T1DM participants is 0.6 mg/kg/min, we will be able to reject the null hypothesis that the difference is zero with probability (power) 0.976. The type 1 error probability associated with this test of this null hypothesis is 0.05.

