10.2.2 Analysis Plan

The correlation between the independent variable $TDD_{insulin}$ (averaged over 7 days prior to each STUDY B-C visit) and the GIR over the last 30 minutes of the clamp will be determined. Several other explanatory variables could confound this bivariate analysis, however. For example, confounding variables might include treatment order, hyperglycemia, hyperlipidemia, or measures of glycemic variability. For this reason, as with STUDY 1-5, I will use multivariable linear regression analysis to account for the effect of these potential confounders.

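### The analysis plans name only correlation and ordinary linear regression for two to four visits per participant, with no participant term or unit of analysis, while the sample sizes rest on within-person comparison

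*Combined protocol and SAP*

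**What the plan says.** Section 10.1.2 relates total daily insulin dose, averaged over the 7 days before each visit, to GIR, %FMD and MVR. It begins with a correlation and then states: "I will use multivariable linear regression analysis to account for the effect of potential confounders". Unadjusted and adjusted linear models are to be compared. Model size is counted in people: "The study accrual of 40 participants provides 3 to 4 degrees of freedom for a multivariable linear regression analysis".

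Section 10.2.2 does the same for GIR in STUDY B-C: "as with STUDY 1-5, I will use multivariable linear regression analysis to account for the effect of these potential confounders". On order effects it says that "confounding variables might include treatment order"; period is not mentioned. Section 10.2.1 again counts people: "At a minimum, 10 participants are needed per degree of freedom to conduct this analysis".

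Section 6.1 gives each T1DM participant three visits (STUDY1-3) and each control four (STUDY 4-7). Section 6.2 gives each Aim 3 participant two clamp visits. Neither analysis section says whether a row is a visit, a participant or a within-person change, or whether the T1DM and control substudies share one regression.

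The sample-size sections do use the pairing. Table 7 lists an "overall standard deviation, and longitudinal correlation, respectively, for each key outcome", with r of 0.79 for GIR and 0.83 for %FMD. For Aim 3, Section 10.2.1 states a null hypothesis on the difference between diets and says "we will be able to reject the null hypothesis that the difference is zero with probability (power) 0.976".

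**The concern.** Dose is defined per visit, so the natural reading is one row per visit. Ordinary regression then treats one person's visits as independent, although the plan itself expects correlations of 0.79 and 0.83 between them. The standard error is wrong, and its direction depends on the comparison. For a dose change within a person it is too large, and power is lost. For a difference between people it is too small, and false positives rise. Total daily dose varies in both ways.

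This affects the primary analyses of all three aims. It also affects the interim stopping rules in Sections 10.1.4 and 10.2.4, which apply a critical z of 2.80 to those analyses. With the unit of analysis and the handling of the two substudies left open, either choice could be made after the data are seen.

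**Working it through.** **1. Reproduce Table 7 as paired contrasts.** Inputs are n = 20, δ, σ and r from Table 7, two-sided α 0.05. SD of the difference = σ√(2(1−r)); noncentral t with 19 df and noncentrality δ√n / SD. For T1DM GIR: 2.7 × √0.42 = 1.75; 1.3 × √20 / 1.75 = 3.32; power 0.883, matching the stated 0.88.

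Ignoring the pairing on the same correlated data inflates the reported standard error by 1/√(1−r): 2.18 at r = 0.79 and 2.43 at r = 0.83. Power was simulated with an unpaired t-test on correlated visits (60,000 data sets).

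| Contrast | SD of difference | Paired | Pairing ignored | Stated |
|---|---|---|---|---|
| T1DM GIR | 1.75 | 0.883 | 0.19 | 0.88 |
| Control GIR | 2.27 | 0.984 | 0.49 | 0.92 |
| T1DM %FMD | 2.51 | 0.961 | 0.23 | 0.88 |
| Control %FMD | 2.16 | >0.999 | >0.99 | 0.83 |

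The last three stated powers do not reproduce from their printed inputs even when paired. That is a separate matter.

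**2. Reproduce Aim 3.** n = 30, difference 0.6, and 0.8 taken as the SD of the within-person difference: 0.6 × √30 / 0.8 = 4.11, power 0.978 against the stated 0.976. Two independent groups of 30 with SD 0.8 would give 0.81. If 0.8 is instead a per-visit SD, the same paired result needs r = 0.5, since 0.8 × √(2 × 0.5) = 0.8. No correlation is given for Aim 3.

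**3. The dose slope in the T1DM substudy alone.** 20 people, 3 visits, SD 2.7, r 0.79, assumed slope −1.3 mg/kg/min per 0.4 units/kg/day, 40,000 runs. The documents give only the Section 6.1 entry windows (STUDY1 0.4-0.6, STUDY2 at most 0.4, STUDY3 at least 0.6 units/kg/day), so the doses are assumed.

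| Assumed STUDY1/2/3 doses | Pooled type I error | Pooled power | Within-person power |
|---|---|---|---|
| Fixed 0.5/0.3/0.7 | 0.0002 | 0.202 | 0.901 |
| Uniform 0.4-0.6/0.2-0.4/0.6-0.8, independent | 0.0006 | 0.288 | 0.921 |
| Same ranges, shared rank | 0.0046 | 0.324 | 0.899 |
| At window edges | 0.034 | 0.430 | 0.901 |
| SD 0.15, clipped to windows | 0.022 | 0.497 | 0.950 |
| STUDY2 0.1-0.4, STUDY3 0.6-1.0 | 0.001-0.006 | 0.655-0.683 | 0.993-0.996 |
| STUDY3 0.6-1.2 | 0.001-0.006 | 0.833-0.870 | >0.999 |

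Within-person type I error is 0.049-0.053 throughout.

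**4. Both substudies in one regression.** 20 × 3 + 20 × 4 = 140 visit rows; control doses assumed 0/0/0.2/0.2 from the glargine and placebo weeks in Section 6.1.1.6; control SD 2.7 or 3.5; r 0.79.

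- Unadjusted: type I error 0.127-0.186, against 0.025-0.054 within person.
- Group term added: at most 0.017; power 0.22-0.94, against 0.94 or more within person.
- T1DM duration added instead (assumed 1-3, 3-6 and 9-12 months; 0 in controls): about 0.01-0.024.

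Counting the overnight infusion as control dose adds 8 mU/m²/min × 480 min × 1.73 m² / 70 kg / 7 days = 0.014 units/kg/day and leaves the unadjusted range unchanged.

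**5. Aim 3 rows.** 40 people × 2 visits = 80 rows, but no insulin regimen is described for the 10 healthy controls. Rows with a described dose: 30 × 2 = 60.

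**The case against.** Within-person intent is visible. Table 7 carries a longitudinal correlation, and Section 10.2.1 states its null hypothesis on a difference between diets. A reader might infer that the plan overlooks pairing altogether. It does not: the defect is that the analysis sections fail to carry the pairing over.

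Counting 40 participants could mean that the participant is the unit. That reading is open, but the count is a model-size rule, the exposure is defined per visit, and no rule for collapsing visits is given.

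A reader might also infer that the planned analysis carries a 13-19% false-positive rate. The documents do not support that. A joint fit is only one possible reading of the count of 40, and the rate applies only to its unadjusted form. Section 10.1.2 lists T1DM duration and HbA1c as covariates, and both track group. Duration brings the error to about 2% or less. HbA1c alone, with the group means and SDs from Section 3.0, brings it to about 5-6%.

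The 0.19 comes from an unpaired test that the plan does not propose, in the worst-affected of four rows; control %FMD loses nothing. The dose-slope figures rest on assumed doses. If doses may stray outside the entry windows (visit means 0.5/0.35/0.7, between-person SD 0.1, within-person SD 0.05), pooled type I error is near 0.05, though power is still 0.49 against 0.92.

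Section 10.2.2 does name treatment order, but as a possible confounder; it is a sequence term, not a participant term. These points limit the size claimed. They do not supply the missing participant term.

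**Conclusion.** The concern holds as a gap between the analysis sections and the sample-size sections. The omission is certain from the text; its size is not.

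- For the T1DM dose slope, with doses inside the entry windows, regression on visit rows is too conservative and power falls to about 0.20-0.50, against 0.90-0.95 within person. With wider STUDY3 doses the loss is smaller (0.66-0.87 against above 0.99).
- The direction of error reverses only if both substudies enter one regression with no covariate that separates the groups.
- All dose-slope and joint-fit figures assume dose distributions and equal correlation between visits.
- The Aim 3 loss cannot be sized, because no within-person correlation is stated, and only 60 of its 80 visit rows have a described dose.

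**What to change.** In Sections 10.1.2 and 10.2.2, replace multivariable linear regression with a linear mixed model that has a participant random intercept, small-sample degrees of freedom and one row per visit. Name the within-participant effect of total daily insulin dose as the term tested; centring dose on each participant's mean is one way to isolate it. Fit the T1DM and control substudies separately, or include a group term if they are fitted together.

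For STUDY B-C, make period and treatment order fixed terms and fit the dose effect in the 30 T1DM participants. State that 0.8 is the SD of the within-person difference, or restate the power.

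The cost is SAP wording and standard software, with no new data or participants. There is one small trade-off: by the plan's own rule of 10 participants per degree of freedom, 30 participants allow 3 terms, which dose, period and order would use up.
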